## 6.3 Subject Population for Analysis

The population whose data will be subjected to the study analysis will include all subjects enrolled in this study that completed the Cytosponge administration and have pathology results available from the subsequent routine care endoscopy with biopsy.

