Objectives	
Primary objective: To assess the acceptability of a novel, minimally invasive esophageal mucosal sampling technique, the Cytosponge, in subjects undergoing surveillance after radiofrequency ablation. Based on previous data, we hypothesize that the sponge-based sampling technique will be associated with low levels of patient distress, and will be preferred by patients, when compared to standard sedated upper endoscopy, for surveillance of their esophageal mucosa.
 
Secondary objective: To assess the operating characteristics of this technique against a gold standard of upper endoscopy with biopsies for endoscopic surveillance in subjects with a history of successful radiofrequency ablation for dysplastic BE. We hypothesize that the assay will demonstrate both a sensitivity and specificity of >90% in the detection of recurrent BE following radiofrequency ablation. Further, we expect higher accuracy in those with a larger burden of recurrent disease.

Number of Subjects	374 (324 Post-ablation, 50 BE)

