### *Secondary objective:*

To assess the operating characteristics of this technique against a gold standard of upper endoscopy with biopsies for endoscopic surveillance in subjects with a history of successful radiofrequency ablation for dysplastic BE. We hypothesize that the assay will demonstrate both a sensitivity and specificity of >90% in the detection of recurrent BE following radiofrequency ablation. Further, we expect higher accuracy in those with a larger burden of recurrent disease.

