### 3.2 Protocol Map

### **3.3 Primary Outcomes**

The primary outcome variables will be sensitivity and specificity of the novel assay, compared against the gold standard of the presence of recurrent BE as detected by upper endoscopy with biopsies.

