# **6 Statistical Plan**

## **6.1 Sample Size Determination**

Previous data suggest a sensitivity of Cytosponge analysis for detecting BE ranging from 84-90%, and a specificity of 92-94%, using upper endoscopy as a gold standard. It is unlikely that this technique will be appropriate for surveillance if the true sensitivity is much lower than 80%, given the unacceptably high rate of false negatives. Previous data document a rate of recurrent BE of 13-38% in subjects assessed with surveillance endoscopy. If we wish to assess the accuracy of the Cytosponge compared to upper endoscopy, assuming a baseline sensitivity of 87%, we will need to enroll 81 subjects with recurrent BE to

yield a 95% confidence interval of 10% or less. If we further assume a rate of recurrent BE of 25% in the post-ablation population, a total of 324 post-ablation subjects will need to be enrolled in the trial.

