## 6.2 Statistical Methods

For the primary objective, to assess the acceptability of the novel mucosal sampling technique in subjects after successful ablation, we will assess the distribution of Impact of Events Scale scores, and the intrusiveness and avoidance subscales. We will generate measures of central tendency and distribution of these data. Bivariate analysis will be performed to assess for predictors of low tolerance of Cytosponge surveillance, and a logistic regression model created to assess these factors while controlling for potential confounders. Data will be compared to population norms using parametric statistics. VAS scores will be calculated, and measures of central tendency and distribution reported.

Subjects' preferences for Cytosponge vs. endoscopic surveillance, as well as willingness to undergo the procedure again, will be measured as proportions, with bivariate and multivariate analyses for predictors of preference performed.

For the secondary objective, to assess the operating characteristics of Cytosponge against a gold standard of upper endoscopy, initially 2x2 tables will be constructed demonstrating Cytosponge and the gold standard findings (Y/N for BE). Sensitivity, specificity, positive predictive value, negative predictive value and accuracy will be calculated. Because Cytosponge positivity may vary based on the burden of BE, we will perform sensitivity analyses, defining "positive" cases as those with recurrent BE of  $\geq 1$  cm in length, and then  $\geq 2$  cm in length, to assess impact of disease burden on operating characteristics. Multivariate models controlling for age, sex, period of time from last ablation, burden of residual disease, and other potential confounders will be constructed, to assess the impact of these factors on test accuracy. Although we do not expect to see an association between the degree of dysplasia and Cytosponge positivity, exploratory analyses will be performed using degree of dysplasia as a predictor variable, and Cytosponge positivity as the outcome variable.

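### Section 6.3 sets one analysis population that ignores the post-RFA scope of both objectives; applied literally, it brings never-ablated BE subjects into the accuracy table and ties acceptability to pathology

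*Combined protocol and SAP*

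**What the plan says.** Section 6.3 is the only statement of who is analysed. The population will "include all subjects enrolled in this study that completed the Cytosponge administration and have pathology results available from the subsequent routine care endoscopy". It separates neither the two cohorts nor the two kinds of endpoint. The Study Summary gives the number of subjects as "374 (324 Post-ablation, 50 BE"; section 3.1 makes 50 a ceiling and describes the BE cohort as a source of pilot data. Exclusion 3 in section 4.2 requires that this cohort has never been ablated.

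The rest of the plan points to the post-RFA cohort:

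- The primary objective (section 2) and the first paragraph of 6.2 place acceptability in patients after successful ablation.
- The secondary objective places accuracy "in subjects with a history of successful radiofrequency ablation for dysplastic BE".
- Section 3.3 has the assay "compared against the gold standard of the presence of recurrent BE as detected by upper endoscopy with biopsies".
- Section 6.1 concludes that "a total of 324 post-ablation subjects will need to be enrolled in the trial".
- In 6.2, the sensitivity analyses define positive "cases as those with recurrent BE of" at least 1 cm, then at least 2 cm, and "Multivariate models controlling for age, sex, period of time from last ablation, burden of residual disease, and other potential confounders will be constructed".

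The main accuracy table is less specific: "2x2 tables will be constructed demonstrating Cytosponge and the gold standard findings (Y/N for BE"). It says BE, not recurrent BE, so its label does not keep the BE cohort out.

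**The concern.** A programmer who builds the dataset from 6.3 would put up to 374 subjects in the 2x2 table. Up to 50 of them cannot have BE recurring after RFA. Nearly all would be expected to be reference-positive, because a current BE diagnosis is how they qualify. PPV and NPV would then reflect a case mix set by how many pilot subjects were recruited, and the sensitivity interval would look tighter than the post-RFA data support. The multivariable models need time since last ablation, which these subjects lack, so the tables (up to 374) and the models (up to 324) would describe different people.

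For acceptability, 6.3 omits the post-RFA limit and adds a pathology condition. The visual analogue scale (VAS) is completed before the endoscopy (section 5 table, footnote 2). The Impact of Events Scale is taken by phone at day 7 and measures distress from the Cytosponge (section 5.2.2). Neither needs a biopsy result, so usable answers would be dropped whenever pathology was missing.

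**Working it through.** **The plan's own figure.** Section 6.1 assumes 81 recurrent cases at 25% recurrence: 81 / 0.25 = 324. This reproduces, and it is a post-ablation count only.

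**Inputs.** Sensitivity 87% (section 6.1). Specificity 93%, the midpoint of the 92-94% in 6.1. Recurrence 25%, with the 13-38% range in 6.1. This gives 81, 42 or 123 post-RFA positives (P) and 243, 282 or 201 negatives (N) out of 324. Assumptions: both cohorts share the same sensitivity and specificity and, in the main case, all 50 BE subjects are reference-positive.

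**Formulas.**

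- PPV = 0.87P / (0.87P + 0.07N)
- NPV = 0.93N / (0.93N + 0.13P)
- Half-width of the sensitivity interval (Wald) = 1.96 × sqrt(0.87 × 0.13 / P)

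**Main case.** BE subjects are 50/374 = 13.4% of records and 50/131 = 38% of positives.

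- Post-RFA only: PPV = 70.47/87.48 = 80.6%; NPV = 225.99/236.52 = 95.5%; half-width 7.3 points.
- With 50 BE positives: PPV = 113.97/130.98 = 87.0%; NPV = 225.99/243.02 = 93.0%; half-width 5.8 points.

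**Range.**

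| Post-RFA P/N | BE subjects added | BE share of positives | PPV | NPV | Half-width (points) |
|---|---|---|---|---|---|
| 81/243 | none | 0% | 80.6% | 95.5% | 7.3 |
| 81/243 | 25 positive | 24% | 84.4% | 94.3% | 6.4 |
| 81/243 | 40 positive, 10 negative | 33% | 85.6% | 93.7% | 6.0 |
| 81/243 | 50 positive | 38% | 87.0% | 93.0% | 5.8 |
| 42/282 | none | 0% | 64.9% | 98.0% | 10.2 |
| 42/282 | 50 positive | 54% | 80.2% | 95.6% | 6.9 |
| 123/201 | none | 0% | 88.4% | 92.1% | 5.9 |
| 123/201 | 50 positive | 29% | 91.5% | 89.3% | 5.0 |

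Under these assumptions the sensitivity estimate itself does not move.

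**Pathology condition.** The plan gives no rate of missing pathology. At an assumed 1%, 5% or 10%, the rule drops 3, 16 or 32 of 324 subjects. For an illustrative preference of 80%, 1.96 × sqrt(0.8 × 0.2 / n) goes from 4.36 points (n = 324) to 4.38 (n = 321), 4.47 (n = 308) or 4.59 (n = 292).

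**Swallowing failures.** Section 1.3.1 reports 3 of 504 in primary care, or 0.6%. Applied to 324, that is 324 × 3/504 = 1.9, about 2 subjects. The documents give no post-RFA rate.

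**The case against.** The best defence is that 6.3 is only a completeness rule: Cytosponge done, pathology in hand. Who enters which analysis is set elsewhere. The 2x2 sentence in 6.2 is introduced as serving the secondary objective, which is limited to post-RFA patients, and the outcome, the sizing and two parts of 6.2 agree. This stands to the extent that a reader should not infer that the plan intends to pool the cohorts. The documents do not say so, and most of them point the other way. It does not rescue 6.3, which is the operative population rule, says all enrolled subjects, and is nowhere qualified by cohort.

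A reader might also infer that pooling would inflate sensitivity. Section 2 does expect better accuracy with more recurrent disease. But the documents report no sensitivity by ablation history, so neither the direction nor the size of any shift can be derived from them.

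On acceptability, it would be too strong to say that the pathology condition is irrelevant to every measure. The preference question sets the Cytosponge against endoscopy with biopsies, and section 3.1 times the day-7 call so that subjects can compare the two. Available pathology is partly evidence that the comparator took place. That supports requiring the same-day endoscopy for preference, but not a pathology result. It is also fair that few subjects should be lost, since footnote 3 of the section 5 table calls these biopsies standard of care.

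**Conclusion.** The point holds as a conflict in the text. As written, 6.3 defines a population that the objectives, outcome, sizing and models do not share. Its effect on accuracy is conditional on a literal application. With 81 recurrences, 50 reference-positive BE subjects and equal test performance in both cohorts, PPV rises by 6.4 points (87.0 − 80.6), NPV falls by 2.5 (95.5 − 93.0), and the half-width narrows by 1.5 (7.3 − 5.8). The PPV shift is larger at 13% recurrence (64.9% to 80.2%) and smaller at 38% (88.4% to 91.5%); it also shrinks if fewer BE subjects enrol or some prove reference-negative. None of these changes describes post-RFA patients.

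The pathology condition is the lesser part. Its precision cost is at most 0.23 points (4.59 − 4.36) at an assumed 10% missing, and any bias cannot be sized from the documents. The 324 itself is unaffected. This should be fixed before analysis because, left open, the choice of population could be made after the results are known.

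**What to change.** Amend section 6.3 to define three sets:

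- **Accuracy:** post-RFA subjects who completed the Cytosponge and have pathology available.
- **Acceptability:** post-RFA subjects with VAS or Impact of Events data, with no pathology condition. For Cytosponge-versus-endoscopy preference, post-RFA subjects who answered the question and had the same-day endoscopy, whether or not pathology is available. Alongside these, report the number and proportion of post-RFA subjects classified as swallowing failures under section 5.1.3. Section 4.4 withdraws these subjects and generally ends their follow-up, so rewording 6.3 cannot supply their day-7 answers.
- **BE pilot cohort:** reported separately and left out of the analyses that answer the primary and secondary objectives. Any pooled analysis is labelled exploratory.

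The cost is a rewording plus one descriptive line. No subjects or procedures are added: ablation history is collected at enrolment, swallowing failure is already a defined category, and withdrawals have their own form. The sensitivity interval is wider than under the literal rule (7.3 against 5.8 points at 81 cases), but it equals what the 324-subject sizing provides.

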*A novel non-endoscopic technique as a potential surveillance tool after successful endoscopic ablation.* Given the large number of patients with chronic GERD and BE, and the expense and inconvenience of endoscopic examinations for BE, investigators have sought less expensive, non-endoscopic modalities of assessing patients for BE. Early attempts using a non-endoscopic balloon demonstrated inadequate sensitivity, in part due to inadequate cytological samples. More recently, a simple, non-endoscopic device, termed the Cytosponge, has been developed for endoscopic screening of subjects at risk for BE by investigators at the University of Cambridge in the U.K. The Cytosponge is an ingestible gelatin capsule enclosing a compressed spherical mesh of 3 cm diameter, the center of which is attached to a string (Figure 4). The capsule and string are swallowed with water. The string is held at the mouth without tension, allowing the capsule to move into the stomach. After 5 minutes (during which the gelatin capsule dissolves and the sponge is liberated), the sponge is withdrawn by gentle traction on the string. The sponge is placed in fixative for 48 hours, then the cells are pelleted, and processed into paraffin blocks. The pellets are immunostained with trefoil factor 3, which is interpreted simply as either positive or negative by the presence of any staining. In a recent study of 504 subjects with chronic GERD symptoms in the U.K. who underwent both Cytosponge analysis and upper endoscopy, the Cytosponge demonstrated a sensitivity of 90% and a specificity of 94% for the detection of BE (Prague classification C2 or more). Follow-up work with an additional 334 subjects (186 controls, 148 BE) demonstrated similar results, with a sensitivity of 84% and a specificity of 92% (data courtesy of [name], MA(Cantab),MD). These results suggest that the Cytosponge may have suitable operating characteristics to serve as a surveillance tool in subjects with BE or dysplastic BE who have undergone ablative therapy.

Figure 4 Cytosponge

Figure 5 CytospongeTM (left) and Cytosponge I (right) for comparisonCytospongeTM (left) and Cytosponge I (right) for comparison

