## 3 Study Design

### 3.1 General Design

This is cross-sectional study of subjects with dysplastic BE who have undergone successful endoscopic ablation with RFA, to assess the utility of the Cytosponge assay as a non-endoscopic method for monitoring the post-ablation patient. In addition, we will enroll a small cohort of up to 50 subjects with a current diagnosis of BE to collect pilot data for a larger scale study. Subjects presenting to UNC Hospitals for routine endoscopic examinations for current BE or after successful ablation will be offered enrollment in the study. After informed consent, and the same day as the endoscopic procedure, the subject will undergo administration of the Cytosponge assay. The patient will then undergo routine endoscopic surveillance, using a standard Seattle biopsy surveillance protocol. The Cytosponge will be placed in fixative and shipped to the [name] laboratory for processing according to their established protocols. Tissue biopsies will undergo standard processing and H&E staining, with assessment by expert gastrointestinal pathologists at UNC. The primary outcome variables will be sensitivity and specificity of the novel assay, compared against the gold standard of the presence of recurrent BE as detected by upper endoscopy with biopsies. Secondary outcomes include acceptability of the nonendoscopic assay to the patient (assessed by a standardized tool, the Impact of Events Scale, as well as a visual analogue scale), and likelihood of assay positivity as a function of amount of residual disease (as measured by Prague criteria).

[figure not shown]
If the initial administration of the Cytosponge demonstrates an inadequate sample, defined as a sample that does not demonstrate at least one columnar cell on hematoxylin & eosin staining, repeat Cytosponge administration will be performed at 30 days (+/- 10 days) from the initial administration.

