### **5.1.3 Cytosponge Administration**

The Cytosponge™ device (referred to hereafter as the "Cytosponge") will be supplied by Covidien GI Solutions to the participating sites. Study sites will be responsible for storage and accountability of the device. The Cytosponge lifetime/use by date will be confirmed on the product packaging. The device received FDA 510(k) clearance on November 26, 2014 (K142695). The Cytosponge device consists of a spherical 3.0 cm diameter reticulated polyester foam compressed and encapsulated in a standard vegetarian capsule (size 00).

Subjects will undergo administration of the Cytosponge™ according to the IFU. Briefly, subjects will be placed in the seated position and will swallow the capsule with 150 – 250 mL of water. Additional water may be used if necessary. The sponge is attached to a length of suture material which passes out through the capsule. The suture is affixed to a retainer card which is held by the subject or administrator to prevent inadvertent swallowing of the suture. The string is to be held without tension as peristalsis and gravity advance the capsule into the stomach.

The capsule dissolves in the stomach, allowing the sponge to expand to its full size. Seven minutes and 30 seconds to ten minutes after ingestion, the sponge is then withdrawn by gentle traction on the suture, collecting cells from the lining of the esophagus in passing.

After retrieval, the string is cut and the retrieved foam sphere containing the cytological specimen is immersed in fixative and stored refrigerated (1° to 12°C [34° to 54°F]) until shipped. Samples will be shipped in batches to the [name] Lab in Cambridge. On arrival at the [name] lab, the fixative is spun in a centrifuge, and the pelleted cells are embedded in paraffin using standard techniques. The blocks are sectioned and stained for trefoil factor 3, where any staining is considered positive for the assay.

If a subject fails to swallow the Cytosponge, the subject will be asked to swallow again. Subjects who are willing to try again will be asked to wait 5 minutes before the Cytosponge is presented to them again. Subjects will be able to try up to three times before they are classified as "Cytosponge swallowing failure" and discontinued by the investigator.

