## **5.3 Repeat Cytosponge Administration**

If the initial Cytosponge sample is inadequate, sites will be notified and subjects will be asked to return for repeat Cytosponge administration 30 days (+/- 10 days) after the initial Cytosponge administration. Only the Cytosponge administration will be repeated. Questionnaires and the endoscopy procedure will not be repeated on these patients. See section 5.1.3 for details on the Cytosponge administration procedure. The Repeat Administration eCRF should be completed.

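### Subjects with no adequate sponge sample after the permitted repeat have no defined place in the accuracy table; read literally, they can enter only as test negatives

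*Combined protocol and SAP*

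**What the plan says.** Section 6.3 defines one analysis population for the whole study: "all subjects enrolled in this study that completed the Cytosponge administration and have pathology results available from the subsequent routine care endoscopy with biopsy". Sample adequacy is not a condition.

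Section 3.1 recognises an inadequate initial sample, "defined as a sample that does not demonstrate at least one columnar cell on hematoxylin & eosin staining". Under Section 5.3 such "subjects will be asked to return for repeat Cytosponge administration 30 days (+/- 10 days) after the initial Cytosponge administration"; the questionnaires and the endoscopy are not repeated.

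On reading the assay, Section 5.1.3 says that sections are stained for trefoil factor 3 (TFF3), "where any staining is considered positive for the assay". The background in Section 1.2 describes the stain as "interpreted simply as either positive or negative by the presence of any staining". Section 6.2 then sets the sponge result against endoscopy in a 2x2 table, yes or no for BE, and derives sensitivity, specificity, predictive values and accuracy from it. It has no third result category.

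No section says what happens to a subject who does not return or whose repeat is also inadequate, and no inadequacy rate is given. Section 3.3 names sensitivity and specificity as the primary outcomes; Section 2 places them under the secondary objective.

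**The concern.** Section 3.1 separates a sample that cannot be interpreted from one that is negative. The analysis sections lose that distinction. Section 6.3 admits the subject, Section 6.2 offers two result cells, and a sample without columnar cells would be expected to show no TFF3 staining. On a literal reading the subject becomes a false negative if BE is present and a true negative if it is not.

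Two different events would then share one number: the assay missing BE in a valid sample, and the device giving no valid sample. Sensitivity would fall and specificity would rise by amounts set by the inadequacy rate. Dropping these subjects without saying so has the opposite fault, because it hides how often the test gives no usable answer. Section 2 hypothesises more than 90% for both measures, so an unwritten choice could affect the conclusion.

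Missed repeats are foreseeable. Sections 4.4 and 5.2 treat participation as complete at the day-7 call, but the repeat falls on days 20 to 40. Subjects are only asked to return, and Section 5.1.3 has sponges shipped in batches, so notice of inadequacy may come late.

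**Working it through.** **Inputs from Section 6.1.** Sensitivity 87% (earlier data 84-90%); specificity 92-94%, taken here as 93%; 81 cases of recurrent BE; 25% recurrence; 324 post-ablation subjects.

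**Assumptions.** The documents give no inadequacy rate, so the final fraction f without an adequate sample is assumed and shown as a range. It is taken as equal in subjects with and without BE, and inadequate samples are taken to be unstained.

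**The plan's own figures.** 81 / 0.25 = 324 reproduces. The 81 itself does not follow from the simple Wald formula at 87%: a half-width of 10 points needs 44 cases and a full width of 10 points needs 174. The plan does not state which width or interval method it used, so this is not called an error, and nothing below depends on it. At n = 81 the Wald half-width is 1.96 x sqrt(0.87 x 0.13 / 81) = 7.3 points.

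**Three ways to handle the same subjects.**
- Counted negative: sensitivity = 0.87(1 - f); specificity = 0.93(1 - f) + f = 0.93 + 0.07f.
- Excluded: 87% and 93%, on a fraction 1 - f of the subjects.
- Counted as failures in both groups: sensitivity = 0.87(1 - f); specificity = 0.93(1 - f).

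| Final f (assumed) | Sensitivity, counted negative or as failure | Specificity, counted negative | Specificity, counted as failure |
|---|---|---|---|
| 2% | 85.3% | 93.1% | 91.1% |
| 5% | 82.7% | 93.4% | 88.4% |
| 7/81 = 8.6% | 79.5% | 93.6% | 85.0% |
| 10% | 78.3% | 93.7% | 83.7% |

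For 7 of 81: 0.87 x 74/81 = 79.5%, and 0.93 + 0.07 x 7/81 = 93.6%. Exclusion leaves 87% on 74 cases, with a Wald half-width of 7.7 points. The two choices differ by 87.0 - 79.5 = 7.5 points, about the planned half-width.

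**From first-pass failure to f.** With first-pass inadequacy r, a proportion q returning, and independent attempts (all assumed), f = r(1 - q) + r²q.
- Full return, r = 5%: f = 0.25%, 0.2 of 81 cases, sensitivity 86.8%.
- Full return, r = 10%: f = 1%, 0.8 cases, 86.1%.
- Full return, r = 20%: f = 4%, 3.2 cases, 83.5%.
- Full return, f = 8.6%: r = sqrt(7/81) = 29%.
- Half return, r = 15%: f = 0.075 + 0.01125 = 8.6%, or 7.0 cases.
- No return: f = r, so r = 8.6% already gives 7 cases.

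The effect therefore depends mainly on how many subjects come back.

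**The case against.** A reader might infer that the plan scores inadequate samples as negative. No section says so. Section 3.1 makes inadequacy its own category, read on H&E rather than on TFF3, and recalls the subject because the result was uninformative. The staining rule in Section 5.1.3 says what is positive and does not mention samples already judged inadequate. A sample with no valid result could fairly be read as contributing no finding to the table. This stands: negative scoring is the literal consequence of Sections 5.1.3, 6.2 and 6.3 taken together, not an express instruction. The alternative reading, however, drops from the accuracy analysis subjects whom Section 6.3 includes, and no section provides for that either.

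Section 6.3 also serves the acceptability analyses. Subjects who swallowed the sponge belong there whether or not the sample was adequate, so the missing condition is not a fault for those analyses. This also stands, and the remedy should leave them in.

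The repeat sponge is a real safeguard and may leave very few unresolved subjects, as the full-return figures show. Equal f in both groups may overstate the loss of sensitivity: adequacy needs a single columnar cell, and BE is itself columnar, so cases have an additional source. Finally, accuracy is the secondary objective in Section 2. These points limit the likely size. They do not supply the missing rule.

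**Conclusion.** The point holds as a gap between Section 3.1, which separates inadequate from negative, and Sections 5.1.3, 6.2 and 6.3, which leave no place for a subject who ends without an adequate sample. The size cannot be estimated from the documents. Under the assumed 7 of 81, with 87% sensitivity and 93% specificity in adequate samples and equal f, counting these subjects negative gives 79.5% and 93.6%, while exclusion gives 87% on 74 cases. With 10% first-pass inadequacy, full return and independent attempts, sensitivity is 86.1% and the issue is minor.

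A reader might also infer that about seven such cases would take the assay below an 80% limit for usefulness. Section 6.1 sets no such limit. It remarks that the technique is unlikely to be appropriate if true sensitivity is well under 80%, and 79.5% is not well under it. The count that brings the figure below 80% also runs from 4 to 10 cases over the protocol's own 84-90% range, so it is not a stable threshold.

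The change is still worth making: the measures affected are the primary outcomes in Section 3.3, and the rule should be fixed before results are seen.

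**What to change.** In Sections 6.2 and 6.3:

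- Keep subjects without an adequate sample in the acceptability analyses.
- For accuracy, state that a TFF3-negative call requires an adequate sample.
- Replace the 2x2 table with a 2x3 table: positive, negative with an adequate sample, and no adequate sample after the permitted repeat (declined, missed, or inadequate again).
- Report sensitivity and specificity among subjects with an adequate sample as the main estimate.
- Add a sensitivity analysis that counts no adequate sample as a failure to give a correct result, in both BE and BE-free subjects. Other conventions exist; this one does not credit specificity for samples that gave no answer.
- Report the inadequacy rate after the first and after the repeat sponge.

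The cost is a few sentences and one more result category. Adequacy of the first sample must already be read to trigger the repeat; Section 3.1 mentions it only for the initial administration, so the text should say that it is read for the repeat as well. The downside is that a second, less favourable accuracy figure will be reported.
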